5.3.3 BCVA Improvement of ≥ 15 Letters from Baseline

The proportion of patients with a BCVA improvement of ≥ 15 letters from baseline in the study eye at each postbaseline visit will be calculated for each treatment group. Between-group comparisons and the 95.1% confidence intervals for the between-group difference will be performed using the same method as described for the primary efficacy variable in Section 5.2.2 for superiority testing using the ITT population.

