7.3.2 Secondary Efficacy Analyses

The secondary efficacy analyses will be performed at week 52 for variables listed in Section 7.2.2 using the ITT and PP populations.

For the key secondary efficacy endpoint (mean change from baseline in BCVA at week 52), the statistical analysis for the non-inferiority test will be based on the PP population [REDACTED]

[REDACTED]
[REDACTED]
[REDACTED]
[REDACTED]

[REDACTED] The difference in mean change from baseline in BCVA between each abicipar arm and ranibizumab (abicipar group minus ranibizumab group) and the corresponding 2-sided 95.1% CI will be calculated based on the MMRM model. The non-inferiority test will be performed using a non-inferiority margin of 5 letters. Non-inferiority of abicipar is established if the lower limit of the CI is > - 5.0 letters. The same [REDACTED] model will be applied to the ITT population and the lower limit of the CI will be compared to the 5-letter margin for non-inferiority testing and to zero for superiority testing.

As a sensitivity analysis, mean change in BCVA will be analyzed using an analysis of covariance (ANCOVA) model, which includes the treatment group, baseline CRT (≤ 400 or > 400 microns), and lesion type of choroidal neovascularization (predominantly classic versus minimally classic or occult) as fixed effects and baseline BCVA as a covariate.

For the analysis of secondary efficacy variables, change from baseline in CRT and change from baseline in NEI-VFQ-25 composite scores, similar analysis procedure will be used as outlined for BCVA above for superiority testing using the ITT population.

For the secondary efficacy endpoint, proportion of patients with a gain of 15 or more letters, a similar analysis procedure will be used as outlined for the primary efficacy variable of stable vision for superiority testing using the ITT population.

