1.1 Primary Study Objectives and Design

The study objectives are to assess the safety and efficacy of abicipar compared with ranibizumab in treatment-naïve patients with nAMD.

The clinical hypotheses are:

- Multiple intravitreal injections of 2 mg abicipar have an acceptable safety profile in treatment-naïve patients with nAMD
- The efficacy of at least 1 of the 2 abicipar regimens is noninferior to that of monthly ranibizumab intravitreal injections as assessed by the proportion of patients with stable vision at Week 52

This is a multicenter, double-masked, randomized, 104-week, parallel-group, activecontrolled study to evaluate the safety and efficacy of abicipar in treatment-naïve patients with nAMD. Approximately 900 patients will be randomized by region with a 1:1:1 allocation ratio to receive one of the following three treatments:

• Treatment group 2Q8: 2 mg abicipar administered at baseline (Day 1) and Weeks 4 and 8, followed by doses at 8-week intervals through Week 96

- Treatment group 2Q12: 2 mg abicipar administered at baseline (Day 1), and Weeks 4 and 12, followed by doses at 12-week intervals through Week 96
- Treatment group rQ4: 0.5 mg ranibizumab administered every 4 weeks from baseline (Day 1) through Week 96

Regions are defined primarily based on geographical locations (eg, North America, EAME [Europe, Africa, and Middle East], Asia Pacific, and Latin America). For randomization purposes, some regions are combined and the following 3 regions are used: North America, Asia, and the rest of the world. The defined 3 regions for randomization will be used for statistical analysis. Within each region, randomization to treatment groups will be stratified by baseline value for best-corrected visual acuity (BCVA \leq 55 versus > 55 ETDRS letters), central retinal thickness (CRT \leq 400 versus > 400 microns), and lesion type of choroidal neovascularization (predominantly classic versus minimally classic or occult) in the study eye.

The study design including treatment and visit schedules is shown in Figure 1 below.

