2.2 Handling Mis-randomization and Mis-stratification

In the event of mis-stratification that resulted in randomization under the wrong stratum, all PP analyses will be based on the actual stratum to which the patient belongs. ITT analysis that uses the randomization stratification factor(s) will be based on the stratum as randomized for the primary efficacy analysis and the actual stratum to which the patient belongs for other analyses such as model-based approaches.

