5.2.2 Primary Analyses of Primary Efficacy Variable

The primary analysis of the primary efficacy variable will be performed using the PP population based on a stratified method with Cochran-Mantel-Haenszel (CMH) weights. Within the framework of this method, the difference in the proportions between each abicipar arm and ranibizumab (abicipar group minus ranibizumab group) and the corresponding 2-sided 95.1% confidence interval for non-inferiority testing will be calculated. Specifically, the confidence intervals for treatment group differences will be calculated using the CMH weighted method with the baseline BCVA (\leq 55 versus > 55 ETDRS letters) as a stratification factor as described in Yan and Su (2010). Missing data for BCVA will be imputed using the last observation carried forward (LOCF). The formal non-inferiority test will be performed at Week 52 with a non-inferiority margin of 10% at an alpha level of 0.049. This alpha reflects an adjustment of 0.001 for the unmasked data review by the data safety monitoring committee (DSMC) for safety assessments. The total alpha spent of 0.001 for the DSMC is based on the assumption of no more than 10 unmasked reviews during the study, with 0.0001 allocated to each review. Thus, the overall alpha for the study is preserved at 0.05 level.

For hypothesis testing, if the lower limit of the 95.1% confidence interval for the difference between an abicipar group and ranibizumab is greater than or equal to -10%, non-inferiority of the abicipar group is established.

Multiplicity for the primary efficacy analysis will be controlled using a gatekeeping procedure defined by the following sequence to control the overall type I error rate at 0.05 level:

- **Step 1:** Testing for non-inferiority of abicipar 2Q8 against ranibizumab
- **Step 2:** Testing for non-inferiority of abicipar 2Q12 against ranibizumab

Hypothesis testing for abicipar 2Q12 against ranibizumab is valid only if non-inferiority for abicipar 2Q8 against ranibizumab is established.

If both abicipar groups have demonstrated non-inferiority to ranibizumab using the PP population, hypothesis testing for superiority will be performed using the ITT population for each abicipar group following the same order as defined above for non-inferiority testing. Superiority of abicipar will be demonstrated if the lower confidence limit for the treatment difference is greater than zero.

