5.3.1 BCVA Mean Change from Baseline

For the key secondary efficacy endpoint mean change from baseline in BCVA at Week 52, statistical analysis for non-inferiority will be based on the PP population using a mixed-effect model for repeated measures (MMRM), which includes BCVA data from baseline (Day 1) to Week 52. The model will include treatment group, region, baseline BCVA in the study eye, baseline CRT ($\leq 400 \ \mu m \ or > 400 \ \mu m$) in the study eye, lesion type of choroidal neovascularization (predominantly classic versus minimally classic or occult) from the confirmation at screening, visit, visit-by-baseline BCVA interaction, and treatment-by-visit interaction as fixed covariates using an unstructured covariance matrix. The difference in

BCVA mean change from baseline between each abicipar arm and ranibizumab (abicipar group minus ranibizumab group) and the corresponding 2-sided 95.1% confidence interval (CI) will be calculated based on the MMRM model. The formal non-inferiority test will be performed at Week 52 using a margin of 5 letters. Non-inferiority of abicipar will be established if the lower limit of the CI is > -5.0 letters. Testing for non-inferiority in mean change will also be performed using the ITT population and the same MMRM model as a sensitivity analysis.

Testing for superiority of abicipar over ranibizumab in BCVA mean change will be performed using the ITT population with the same MMRM model.

As a sensitivity analysis, BCVA mean change will be analyzed using an analysis of covariance (ANCOVA) model, which includes the treatment group, region, baseline CRT ($\leq 400 \text{ or} > 400 \text{ microns}$), and lesion type of choroidal neovascularization (predominantly classic versus minimally classic or occult) from the confirmation at screening as fixed effects and baseline BCVA as a covariate. In this model, missing data will be replaced by LOCF and the analysis will be performed for the PP population. Treatment differences between each abicipar group and ranibizumab and the corresponding 2-sided 95.1% confidence intervals for the difference will be calculated based on the least–square means and appropriate contrasts from the same ANCOVA model.

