5.3.2 SD-OCT CRT Mean Change from Baseline

The electronic SD-OCT images will be evaluated and graded by the Fundus Photograph Reading Center (FPRC). The graded results will be captured on the evaluation form and used for statistical analysis. In the event of excess fluid at baseline and ungradable images that result in missing baseline CRT, the manual read data for retinal thickness at the center point, if available, will be used for analysis.

CRT is measured as the thickness of the subfields, which is the central 1000 μ m from the center of the fovea.

Analysis of CRT mean change from baseline in the study eye will be performed using the same MMRM model for superiority testing based on the ITT population as described in

Section 5.3.1 for the key efficacy variable of BCVA change. The only difference is that baseline CRT will be included in the model as a continuous variable instead of a dichotomy (eg, $\leq 400 \ \mu m$ or $> 400 \ \mu m$) as used for randomization.

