5.3.4 NEI-VFQ-25 Mean Change from Baseline in Composite Score

The NEI-VFQ-25 will be administered at the Baseline/Day 1, and at Weeks 12, 24, 36, 52, 76, and 104/early exit visits. Detailed analyses and analysis visit windows are described in Section 7 for health outcome data analysis.

As a secondary efficacy variable, change from baseline at Week 52 in the overall composite score will be analyzed for superiority testing using the ITT population and MMRM as described in Section 5.3.1 for the key secondary efficacy variable of BCVA change. The model will include the treatment group, region, baseline BCVA in the study eye, baseline VFQ score, visit, and treatment-by-visit interaction as fixed covariates using an unstructured covariance matrix. Treatment differences and the corresponding 95.1% confidence intervals will be constructed using the MMRM model.

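### Adjusting the 15-letter-gain superiority test for region, CRT and lesion type as well as BCVA would recover a little power; the planned test is valid but slightly conservative

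*SAP*

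**What the plan says.** **Randomization.** SAP 1.1 defines three regions and then states: "Within each region, randomization to treatment groups will be stratified by baseline value for best-corrected visual acuity" (55 or fewer v more than 55 letters), CRT (400 or less v more than 400 microns) and lesion type (two classes). That makes 3 x 2 x 2 x 2 = 24 cells. The same section says the three regions will be used in the statistical analysis.

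**15-letter gain.** SAP 5.3.3 has it "performed using the same method as described for the primary efficacy variable in Section 5.2.2 for superiority testing using the ITT population". In SAP 5.2.2, "the confidence intervals for treatment group differences will be calculated using the CMH weighted method with the baseline BCVA" cut at 55 letters as the stratification factor, and no other factor is named. Protocol 7.3.2 agrees: "a similar analysis procedure will be used as outlined for the primary efficacy variable of stable vision for superiority testing using the ITT population". The SAP is headed 150998-005 and the protocol is 150998-006, but they do not differ on this point.

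**The other three secondary endpoints** (SAP 5.3.1, 5.3.2 and 5.3.4).
- BCVA change: "The model will include treatment group, region, baseline BCVA in the study eye, baseline CRT" category and lesion type, with BCVA not cut.
- CRT change: the "same MMRM model for superiority testing based on the ITT population", with CRT made continuous.
- NEI-VFQ-25: "The model will include the treatment group, region, baseline BCVA in the study eye, baseline VFQ score" and visit terms. CRT and lesion type are not listed.

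So 15-letter gain alone lacks region and alone cuts BCVA. It is not alone in omitting CRT and lesion type.

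**The concern.** Stratified randomization balances region, CRT and lesion type between arms. If those factors predict a 15-letter gain, the balance makes the estimated difference vary less from trial to trial. An interval that stratifies only by BCVA gives no credit for this, so it is too wide and the superiority test rejects less often than its nominal level allows. The endpoint is derived from the same BCVA scores as the key secondary endpoint, for which the SAP adjusts for all four factors.

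What is at stake is a modest amount of power and interval width on one secondary endpoint. The stated power for stable vision is not affected.

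**Working it through.** **1. The plan's own figure.** SAP 1.2 gives 240 per group, 90% in both groups, a 10% margin, two-sided alpha 0.05 and about 95% power.
- n = (1.960 + 1.645)^2 x 2 x 0.9 x 0.1 / 0.1^2 = 234, close to 240.
- Power at 240: SE = sqrt(0.18/240) = 0.0274; 0.1/0.0274 - 1.960 = 1.69, so 95.5% (95.4% at alpha 0.049).
- 720/0.8 = 900, or 300 per arm for ITT.

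The figure reproduces. No power is stated for 15-letter gain.

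**2. Closed-form baseline for 15-letter gain.** Rates are assumed. With 300 per arm and z = 1.9686 (alpha 0.049):
- 25% v 37%: SE = sqrt((0.1875 + 0.2331)/300) = 0.0374; half-width 7.37 points (simulated planned analysis 7.38); power about 89%.
- 25% v 33%: SE 0.0369; 0.08/0.0369 - 1.9686 = 0.20; power about 58%.
- 35% v 43%: SE 0.0397; power about 52%.

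**3. Power change from adjustment.** The simulation used 900 patients, blocks of 6 in 24 strata, and two of the three arms compared. Planned analysis: the SAP Appendix A interval over two BCVA strata. Adjusted analysis: a risk difference standardised from a logistic model with region, CRT stratum, lesion type and continuous BCVA, with a robust variance. Assumed mix: regions 45/20/35%, CRT above 400 in 45%, predominantly classic in 30%. There were 12,000 runs per case; the paired SE was 0.06 to 0.23 points. Entries are percentage points, by the odds ratio given to region, CRT and lesion type together:

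| Rates | BCVA | 1 | 1.5 | 2 | 3 |
|---|---|---|---|---|---|
| 25 v 37% | not prognostic | +0.02 | +0.38 | +1.16 | +2.29 |
| 35 v 47% | not prognostic | -0.21 | +0.38 | +1.23 | +2.83 |
| 25 v 33% | not prognostic | +0.37 | +0.88 | +2.50 | +5.33 |
| 35 v 43% | not prognostic | -0.16 | +0.96 | +2.25 | +6.32 |
| 25 v 37% | 1.5 per SD | +0.51 | +0.88 | +1.31 | +2.56 |
| 35 v 47% | 1.5 per SD | +0.47 | +1.17 | +1.61 | +2.98 |
| 25 v 33% | 1.5 per SD | +0.69 | +1.46 | +2.70 | +5.92 |
| 35 v 43% | 1.5 per SD | +0.62 | +1.37 | +2.62 | +5.85 |

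With only one of the three factors prognostic, at an odds ratio of 2 to 3, the 12-point cases gain 0.3 to 1.5 points.

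**4. Interval width at 25% v 37%.** Planned 7.38; adjusted 7.29, 7.16 and 6.88 at odds ratios 1.5, 2 and 3. In interval width this equals about 2.5%, 6% and 15% more patients: (7.38/7.29)^2 = 1.025, (7.38/7.16)^2 = 1.062, (7.38/6.88)^2 = 1.151.

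**5. Mechanism and error rate.** At 35% v 47%, all factors at 3 and regions 60/10/30%, the planned half-width is 7.83 while z times the estimate's empirical SD is 7.30. Adjusted, these are 7.31 and 7.27. Under the null (20,000 runs, factors at 2 to 3, nominal one-sided 2.45%), rejection is 1.60-2.21% planned and 2.31-2.61% adjusted.

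**6. Separate check with other assumptions.** A 10-point effect, 5,000 runs. With a 30% control rate, power goes from 72.6% to 73.0% with no covariate effect, 74.6% to 75.5% with moderate effects and 75.6% to 79.0% with strong effects. The strong case also sets an odds ratio of 2^1.5 = 2.8 between the extreme regions. Replacing the 55-letter cut by continuous BCVA contributes at most about 0.6 point.

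**7. Why not use CMH over all 24 cells.** The Appendix A variance adds 2 responders and 4 patients to each cell. For stable vision there are 240/24 = 10 per arm per cell. With 9 of 10 stable, p* = 11/14 and p*(1 - p*) = 0.168, giving a half-width of 1.9686 x sqrt(2 x 0.168/240) = 7.4 points. With two strata, p* = 110/124 gives 0.100 and 5.7 points. Simulation over unequal cells gave 7.03-7.19 v 5.64-5.66, and power 85.4-86.6% v 94.3-95.0%. For 15-letter gain the 24-cell route changed power by -1.5 to +1.1 points.

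**The case against.** The plan follows a plain pattern: repeated-measures models for continuous endpoints, one CMH method for binary ones. 15-letter gain stands apart partly because it is the only binary secondary endpoint. This is a fair account of how the choice arose, though the visible text gives no reason for leaving out three randomization factors.

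The benefit is small and rests on assumed inputs. This stands. Every power case also supposes that abicipar beats monthly ranibizumab by 8 to 12 points, in a trial built on non-inferiority. If there is no difference, adjustment only moves the rejection rate back to nominal. A little of the gain comes from dropping the +2/+4 term: at most 0.25 points in the 12-point cases, not bounded separately in the 8-point cases.

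SAP 5.2.4.2 and Section 10 are referred to but not visible, and parts of Protocol 7.3 are redacted. A supportive adjusted analysis, a rationale, or this endpoint's place in the testing sequence may be there. Only BCVA mean change is labelled key secondary.

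A reader might infer that the planned test is invalid, or that SAP 1.1 on using the regions contradicts 5.3.3. Neither is supported: the test errs on the conservative side, and SAP 1.1 does not say that every analysis must include region. Nor does the point carry over to changing the primary analysis, whose stated power reproduces with the method as planned.

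**Conclusion.** The point holds as an optional efficiency improvement. The planned 15-letter-gain test is valid and slightly conservative. Adjusting for the factors already used in randomization, with BCVA uncut, changes power by about 0 points if they are not prognostic. It adds about 0.4 to 3 points if region, CRT and lesion type each carry odds ratios of 1.5 to 2. A reader might take the 5- to 6-point entries as the expected gain. They require all three factors at an odds ratio of 3 together with an 8-point effect, and nothing in the documents supports that combination. All of these sizes depend on assumed gain rates, effects, case mix and prognostic strength.

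**What to change.** Before unmasking for the week 52 analysis, amend SAP 5.3.3 for 15-letter gain at week 52 (ITT, same LOCF data):
- Main analysis: a risk difference standardised from a logistic model with treatment, region, CRT stratum, lesion type and continuous baseline BCVA, with a robust 95.1% interval.
- BCVA-only CMH interval as sensitivity analysis, and as fallback on non-convergence. Simulated non-convergence was under 0.01% at response rates of 25-47%.
- Strata: SAP 2.2 already assigns "the actual stratum to which the patient belongs for other analyses such as model-based approaches", so no new rule is needed.
- Do not extend the Appendix A interval to 24 strata.
- Leave the stable-vision method and decision rule unchanged; the adjusted estimate may be shown beside it as supportive.

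The cost is some programming and no new data. Protocol 7.3.2 ties this endpoint to the stable-vision procedure and SAP Section 11 declares no deviations, so either the protocol wording is matched or a deviation is declared. The estimator would differ from that for stable vision and, unless the model is also used there, from the other visits in 5.3.3. If the BCVA-only analysis is kept, and no reason stands in the text that is not visible, one sentence saying why is enough.

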5.3.4 NEI-VFQ-25 Mean Change from Baseline in Composite Score

The NEI-VFQ-25 will be administered at the Baseline/Day 1, and at Weeks 12, 24, 36, 52, 76, and 104/early exit visits. Detailed analyses and analysis visit windows are described in Section 7 for health outcome data analysis.

As a secondary efficacy variable, change from baseline at Week 52 in the overall composite score will be analyzed for superiority testing using the ITT population and MMRM as described in Section 5.3.1 for the key secondary efficacy variable of BCVA change. The model will include the treatment group, region, baseline BCVA in the study eye, baseline VFQ score, visit, and treatment-by-visit interaction as fixed covariates using an unstructured covariance matrix. Treatment differences and the corresponding 95.1% confidence intervals will be constructed using the MMRM model.

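### The NEI-VFQ-25 MMRM omits CRT category and lesion type, two of the four randomisation factors, although the BCVA MMRM it refers to includes both

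*SAP*

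**What the plan says.** **Randomisation.** SAP 1.1 randomises by three regions. Within region it stratifies by baseline BCVA (≤ 55 / > 55 letters), CRT (≤ 400 / > 400 microns) and CNV lesion type (predominantly classic against the other two classes).

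**BCVA model, SAP 5.3.1.** The term list begins "The model will include treatment group, region, baseline BCVA in the study eye, baseline CRT". It goes on to lesion type, as confirmed at screening, and visit, and ends with "visit-by-baseline BCVA interaction, and treatment-by-visit interaction as fixed covariates using an unstructured covariance matrix".

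**CRT model, SAP 5.3.2.** This reuses the 5.3.1 model and declares its departure: "The only difference is that baseline CRT will be included in the model as a continuous variable instead of a dichotomy".

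**NEI-VFQ-25 model, SAP 5.3.4.** The composite score is tested for superiority in the ITT population using "MMRM as described in Section 5.3.1 for the key secondary efficacy variable of BCVA change". The terms are then listed: "The model will include the treatment group, region, baseline BCVA in the study eye, baseline VFQ score, visit, and treatment-by-visit interaction". The section also sends the reader elsewhere: "Detailed analyses and analysis visit windows are described in Section 7 for health outcome data analysis".

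**Protocol 7.3.2.** For CRT and NEI-VFQ-25 it says "similar analysis procedure will be used as outlined for BCVA above for superiority testing using the ITT population". The BCVA model whose terms can be read there is the sensitivity ANCOVA. It contains treatment, CRT category and "lesion type of choroidal neovascularization (predominantly classic versus minimally classic or occult) as fixed effects and baseline BCVA as a covariate".

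**The concern.** SAP 5.3.4 cites a model with all four randomisation factors and then lists one with two of them. Where SAP 5.3.2 departs from 5.3.1 it says so, whereas 5.3.4 announces no departure. A reader cannot tell whether the shorter list was a decision or an oversight.

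The statistical consequence concerns efficiency. Stratified randomisation balances the arms on CRT category and lesion type, so the true variance of the treatment difference excludes the variation those factors explain. If the model leaves them out, that variation stays in the residual. The estimated standard error is then too large for the design, the interval is wider than it needs to be, and the superiority test runs slightly below its nominal level.

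**Working it through.** **1. Factors in each model**

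| Term | Randomisation (SAP 1.1) | BCVA MMRM (5.3.1) | CRT MMRM (5.3.2) | NEI-VFQ-25 MMRM (5.3.4) |
|---|---|---|---|---|
| Region | yes | yes | yes | yes |
| Baseline BCVA | yes | yes | yes | yes |
| CRT | yes, category | yes, category | yes, continuous | **no** |
| Lesion type | yes | yes | yes | **no** |
| Visit-by-baseline BCVA | – | yes | yes | **no** |
| Baseline VFQ score | – | – | – | yes |

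The count is four of four factors in 5.3.1 and 5.3.2, and two of four in 5.3.4.

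**2. Size of the loss**

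The plan gives no SD, effect size or power for NEI-VFQ-25, so there is no stated figure to reproduce. The size is therefore shown over an assumed range.

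Inputs:
- Two-sided alpha 0.049 (SAP Section 9), so z = Φ⁻¹(1 − 0.049/2) = 1.9686.
- A nominal 80% power test as reference (assumption), so z_β = 0.8416 and z + z_β = 2.8102.
- R² = share of residual variance explained by CRT category and lesion type once region, baseline BCVA and baseline VFQ score are in the model. Assumed 1%, 3% and 5%.

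Under balanced strata the true variance is (1 − R²) times the variance that the listed model reports. Hence:
- CI narrowing from adding the terms = 1 − √(1 − R²)
- Power of the listed model = Φ(z_β / √(1 − R²))
- Power with the terms added = Φ((z + z_β)/√(1 − R²) − z)
- Type I error of the listed model = 2 × [1 − Φ(z/√(1 − R²))]

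At R² = 5%, √0.95 = 0.9747:
- Narrowing: 1 − 0.9747 = 2.5%
- Listed power: Φ(0.8416/0.9747) = Φ(0.8635) = 80.6%
- Adjusted power: Φ(2.8102/0.9747 − 1.9686) = Φ(0.9146) = 82.0%
- Type I error: 2 × [1 − Φ(1.9686/0.9747)] = 2 × [1 − Φ(2.0197)] = 4.3%

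| Assumed R² | CI narrower by | Power, listed | Power, terms added | Gain (points) | Type I error, listed (nominal 4.9%) |
|---|---|---|---|---|---|
| 1% | 0.5% | 80.1% | 80.4% | 0.3 | 4.8% |
| 3% | 1.5% | 80.4% | 81.2% | 0.8 | 4.6% |
| 5% | 2.5% | 80.6% | 82.0% | 1.4 | 4.3% |

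The reference point matters little. If the adjusted model is set at 80% power instead, the listed model has Φ(2.8102 − z/√(1 − R²)). That is Φ(0.8317) = 79.7% at R² = 1% and Φ(0.7905) = 78.5% at 5%, a loss of 0.3 and 1.5 points.

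**3. Simulation check**

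A single-visit ANCOVA stood in for the Week 52 contrast, with 300 per arm, 24 equal strata, 20% missing at random and 20,000 trials per setting. At R² = 5% it gave power of 80.2% for the listed model and 81.8% with the terms added, a type I error of 4.50% for the listed model, and an interval 2.5% narrower. With R² = 0, adding the terms widened the interval by about 0.05%. The check assumed blocks of 4, which cannot be balanced across three arms at 1:1:1, and it did not model the Week 12, 24 and 36 visits. It is rough support only; the closed-form results do not depend on it.

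**The case against.** The strongest reply is that the plan never promises to put every randomisation factor in every model. The primary CMH analysis (SAP 5.2.2) stratifies by baseline BCVA alone, the ≥ 15-letter endpoint (5.3.3) uses the same method, and the Protocol's ANCOVA omits region. On this reading, 5.3.4 cites 5.3.1 for the method and then gives a complete list suited to its own endpoint. It does not call the model the same, as 5.3.2 does, and an analyst would fit the list. Much of this stands: the model is usable as written, and the mismatch is not a strict contradiction. But the BCVA-only CMH analyses are no reason to leave the two factors out of a regression model whose parent model already carries them.

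Three limits also stand:
- Section 7 of the SAP is not visible and may hold a reason or a fuller model.
- The Protocol is weak support. It promises a similar procedure, not the same one, and its MMRM covariates are redacted. It is for study 150998-006, while the SAP is labelled 150998-005. Protocol 5.4 is redacted, so the four-factor list rests on the SAP. The comparison of 5.3.1 with 5.3.4 lies within the SAP and needs nothing from the Protocol.
- The R² values are assumptions. Zero is equally compatible with the documents, and then there is no gain.

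**Conclusion.** The point holds as a minor improvement. SAP 5.3.4 leaves CRT category and lesion type out of the NEI-VFQ-25 model, although the trial randomises on both and the other two MMRM endpoints adjust for both. No reason is visible.

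No conclusion is put at risk: the listed model is valid and errs, if at all, on the conservative side. The likely cost is small, at most 1.4 power points and 2.5% of CI width over the assumed range of 1% to 5%. It rests on strata that are balanced across arms and on an R² that the documents do not supply. The case for acting is that the possible gain, though small, comes with almost no downside, and that the edit removes a doubt about which model is meant.

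**What to change.** In SAP 5.3.4, add CRT category and lesion type as fixed effects. The term list would then be: treatment; region; study-eye baseline BCVA; CRT category (≤ 400 / > 400 microns); lesion type as confirmed at screening, in the two classes used for randomisation; baseline VFQ score; visit; treatment × visit. Use each patient's actual stratum, as SAP 2.2 already sets for model-based ITT analyses.

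In the same edit, state whether omitting the visit-by-baseline interaction of 5.3.1 is intended. If Section 7 already justifies the shorter list, cite it in 5.3.4 and qualify the reference to 5.3.1.

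The cost is one sentence and two model terms. Both factors are already collected and used in 5.3.1. The primary and key secondary tests, the CMH analyses, alpha, sample size and data collection do not change.
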